| 12/17/09 | On Hold removed. Study renewal (CF footer replaced) due to Continuing Review # 7 (Note: 6-month IRB approval: expires 06/01/10) | 12/01/09 | - |
| 04/01/10 | Front Sheet replaced due to Amendment #37 | 04/01/10 | - |
| 05/26/10 | Study renewal (CF footer replaced) due to Continuing Review # 8 (Note: 6-month IRB approval: expires 11/13/10) | 05/13/10 | - |
| 08/03/10 | Front Sheet replaced due to Amendment #38 | 08/03/10 | - |
| 10/12/10 | Consent Form replaced due to Adverse Event # 23 | 08/26/10 | - |
| 10/14/10 | Patient Info Letter added due to Amendment #39 | 10/14/10 | - |
| 10/27/10 | Permanent Closure to New Accrual: extended period of time lapsed since temporary closure. Analysis will proceed w/ data collected from 330 pts (Effective: 10/13/10; Amendment # 40) | 10/19/10 | - |
| 10/28/10 | BIDMC site ON HOLD due BIDMC Strategic Hold OE #30 | N/A | - |
| 11/12/10 | Study renewal due to Continuing Review #9 | 10/14/10 | - |
| 11/12/10 | Front Sheet replaced due to Amendment #41 | 10/28/10 | - |
| 01/26/11 | Request to remove administrative hold at BIDMC due to Amendment #43 | 01/25/11 | - |
| 02/16/11 | Amendment # 44 (No changes to online documents) | 02/04/11 | - |
| 02/28/11 | Patient Info Letter replaced due to Amendment #42 | 02/03/11 | - |
| 04/20/11 | Patient Info Letter replaced due to Amendment #45 | 04/18/11 | - |
| 09/20/11 | Study renewal due to Continuing Review #10 | 09/15/11 | - |
| 04/27/12 | Protocol, Front Sheet and Patient Information Letter replaced due to Amendment #46 | 04/16/12 | - |
| 07/30/12 | Study renewal/ Consent Form footer replaced due to Continuing Review #11 | 07/26/12 | n/a |
| 08/13/12 | Front Sheet replaced due to Amendment #47 | 08/06/12 | N/A |
| 10/26/12 | Front Sheet replaced due to Amendment #48 | 10/25/12 | N/A |
| 01/15/13 | Patient Survey added due to Amendment #49 | 01/02/13 | N/A |
| 01/15/13 | Correction Am#49: Patient survey removed | N/A | N/A |
| 07/26/13 | ON HOLD: All research must stop due to lapsed Continuing Review. Study expired 07/26/2013 | N/A | N/A |
| 08/08/13 | On Hold removed. Study renewal (CF footer replaced) due to Continuing Review #12 | 08/06/13 | N/A |
| 08/06/14 | ON HOLD: All research must stop due to lapsed Continuing Review. Study approval expired 08/06/14. | N/A | N/A |

| 08/06/14 | Remove Hold. Study renewal/ Consent Form footer replaced due to Continuing Review #13 | 08/05/14 | N/A |
|-------------|---|-------------------|---------------------|

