Therefore, our goal originally was to conduct a study of the feasibility of performing PBI in a selected patient population with external-beam radiotherapy, using 3D-conformal radiotherapy techniques and CT-guided planning that are widely available to and used by radiation oncologists in both academic and community settings. If successful, this approach would provide a readily exportable treatment technique that could be tested against conventional whole-breast irradiation in a randomized trial.

We have accrued 100 patients for the 32 Gy / 8 fractions level in about 2 years and we did not have significant toxicity at 1-year follow-up, which would require the protocol to be closed. We have gained more experience. We believe that the approach we used will provide a readily exportable simple treatment technique that could be tested against conventional whole-breast irradiation in the randomized trial. This study is conducted in the member hospitals of the Dana-Farber/Harvard Cancer Center and Boston Medical Center.

After showing that the technique we used is feasible, our goal is to estimate the optimal radiation dose, which could be used in PBI with the least possible toxicity. Therefore, we started escalating the dose from 32 Gy / 8 fractions, into 36 Gy and 40 Gy in 9 and 10 fractions, respectively (see rationale for dose escalation in section 1.5.2.). At this time, we have accrued 100 patients to the second cohort and 94 patients to the third cohort. We have not seen any significant toxicity from the 40 Gy / 10 fractions requiring the protocol to stop abruptly. We will increase the number of the third cohort from 100 to 200 patients and our primary endpoint of this expanded cohort will be limited to fat necrosis requiring surgery within 3 years of protocol registration. For analyzing this endpoint, all patients who receive 40 Gy (200 patients) will be considered. For details see statistical section (Section 10.0)."

1.4 Video based PBI setup:

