2.0 Objectives

2.1 Primary Objective

To evaluate the feasibility of PBI directed XRT in selected stages 0 and I female breast cancer patients within each dose level. The study will be deemed infeasible if the total percent of patients who have at least one of the following outcomes is large:

- a) Within 1 year of protocol registration, the patient develops histological fat necrosis or other grade 4 skin or grade 4 subcutaneous toxicity, or requires surgery for her skin or subcutaneous toxicity
- b) Within 1 year of protocol registration, the patient develops any breast cancer recurrence or for any reason has additional ipsilateral breast surgery or other ipsilateral breast treatment
- c) Within 1 year of protocol registration, the patient dies from causes judged to be related to her treatment.
- d) Within 3 years of protocol registration, the patient treated with 40 Gy develops fat necrosis requiring surgery.

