5.1 Dose Adjustments/Delays/Modifications/Removal from study

5.1.1 **Treatment Breaks/Interruptions:** Radiotherapy is given in continuous course. It is not anticipated that treatment breaks should be needed. If a break seems necessary or must be given due to unavoidable medical necessity (i.e., intercurrent illness), the situation should be discussed with [name] or [name].

5.1.2 **Removal From Study:** [name] or Research Nurse Manager [name] [contact]) or CRA [name] [contact]) should be notified within 48 hours by telephone or e-mail and within 7 working days by writing of the removal of a patient from protocol.

5.1.3 **Inability to Adequately Perform Treatment Planning:** If the radiation oncologist cannot adequately identify the tumor bed or is otherwise unable to devise a dosimetrically-satisfactory treatment plan, then the patient will be removed from study.

5.1.4 **Recurrence During Treatment:** Any evidence of local, regional or distant recurrence during the period of therapy will result in removal from study. Further, local-regional and systemic therapy will be at the discretion of the attending physicians. Patients who develop recurrence subsequent to the completion of the treatment program will be managed as deemed appropriate by the attending physicians.

5.1.5 **Undue Toxicity:** Refer below. Treatment may be terminated prior to its planned completion should the attending physicians feel that the patient is suffering undue toxicity. Such situations should be discussed with [name] or [name] before removing the patient from study.

5.1.6 **Patient Refusal to Continue Treatment:** A patient may withdraw her consent to participate at any time. In this case, alternative therapy, or no further therapy, may be given at the discretion of the attending physician.

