At this time, the number of patients in the third cohort will be increased from 100 to 200 patients. All patients in this cohort will be treated with the same dose as the third cohort (40 Gy). For analyzing our endpoints, all patients in the third cohort will be combined (for a total of 200 patients). Our primary endpoint for this expanded cohort will be limited to fat necrosis requiring surgery within 3 years of protocol registration.

We expect that 90% of the 200 patients will be available for assessing fat necrosis for 3 years after registration (with the remaining 10% having a recurrence, developing metastases, dying, or being lost to follow-up before the end of 3 years). If more than 5% of the 180 patients (i.e., more than 9 patients) have fat necrosis requiring surgery by 3 years after registration, then the dose of 40 Gy will be considered too toxic. Using this design, if the true probability of this toxicity is 3%, then there will be a 0.05 chance of declaring this dose too toxic; if the true probability of this toxicity is 9% then there will be a 0.97 chance of declaring this dose too toxic.

If none of the 180 patients have this toxicity, the 95% confidence interval (CI) for the probability of fat necrosis requiring surgery will be 0 to 1.7%; if 9 of the 180 patients have this toxicity, a 95% CI will be 2.3 to 9.3%.

The old stopping rule (based on bad events occurring within the first year after registration) will still be in force for the third cohort (these patients have not all yet been followed for a year). That is, all accrual to this protocol will end if 6 or more of the first 50 patients in the third cohort have a "bad event" within a year of protocol registration or if 9 or more of the 100 patients in the third cohort have a "bad event" within a year of protocol registration.

There could be a first interim analysis of the events when the first 50 patients for the 40 Gy dose level have been followed for at least 1 year. Other analysis can follow if the information is deemed by the PI as worthwhile to be published.

11.0 Accrual Rate:

This study has been designated by the Dana Farber/Harvard Cancer Center (DF/HCC) as a rapidly accruing study. We expect an average of 40-50 patients per year to enter this study. If accrual in any 12-month period drops below 20 patients, we will consider terminating the study for lack of accrual.

References

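### The 0.05 and 0.97 error rates for the 40 Gy toxicity verdict belong to about 180 evaluable patients; closure at 330 leaves about 130 at 40 Gy (inferred), and the supplied Section 10.0 does not restate them

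*Combined protocol and SAP*

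**What the plan says.** The rule for the expanded 40 Gy cohort is in Section 10.0. It expects 90% of 200 patients, that is 180, to be assessable at 3 years, and sets the condition for calling the dose too toxic: "If more than 5% of the 180 patients (i.e., more than 9 patients) have fat necrosis requiring surgery by 3 years after registration". It attaches a 0.05 chance of that verdict at a true rate of 3% and 0.97 at 9%. It also gives 95% intervals of 0 to 1.7% for 0 events in 180 and 2.3 to 9.3% for 9 in 180.

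This is a primary endpoint. Section 2.1, item d, reads "Within 3 years of protocol registration, the patient treated with 40 Gy develops fat necrosis requiring surgery", and the end of Section 1.3 says "For analyzing this endpoint, all patients who receive 40 Gy (200 patients) will be considered".

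On numbers, Section 1.3 reports "We have accrued 100 patients for the 32 Gy / 8 fractions level" and, when the cohort was expanded, "we have accrued 100 patients to the second cohort and 94 patients to the third cohort". The revision log at the front records permanent closure to accrual, effective 10/13/10 under Amendment #40: "Analysis will proceed w/ data collected from 330 pts". An entry posted 04/27/12 reads "Protocol, Front Sheet and Patient Information Letter replaced due to Amendment #46". The supplied Section 10.0 still gives error rates for 180 only.

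**The concern.** The error rates and the threshold of 9 were worked out for a cohort that was not reached. A reader of Section 10.0 has only the pair 0.05 and 0.97 by which to judge a verdict on 40 Gy, and that pair does not describe a cohort of about 130. The text also gives the threshold as a percentage and as a count. These agree at 180 but separate at smaller numbers, and nothing says what happens when fewer than 180 are evaluable. At stake are the stated reliability of the verdict and, for some event counts, the verdict itself.

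A smaller matter is that the two intervals share one 95% label but follow different conventions.

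**Working it through.** **Inputs.** Planned evaluable 0.90 × 200 = 180, the threshold, and the true rates of 3% and 9% (Section 10.0); 100, 100 and 94 patients by dose at expansion (Section 1.3); 330 at closure (revision log).

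**1. The plan's own figures.** With X ~ Binomial(n, p), too toxic at n = 180 means X ≥ 10:
- P(X ≥ 10 | 180, 0.03) = 0.0461, stated as 0.05
- P(X ≥ 10 | 180, 0.09) = 0.9670, stated as 0.97

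Both reproduce. To two decimals the pair also holds at 181 to 185 evaluable (0.0505 and 0.9715 at 183), where both wordings still need 10 events.

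**2. Size of the 40 Gy cohort.** 330 − 100 − 100 = 130. This fits 294 at expansion (100 + 100 + 94) plus 36 more. Reaching 180 evaluable at 40 Gy on top of the 200 at lower doses would have taken at least 380 patients. The plan's 90% share gives 0.9 × 130 = 117 evaluable. I take 80% to 100% as an assumed range, 104 to 130.

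**3. Error rates at the smaller size.** The percentage form needs floor(0.05n) + 1 events; the count form needs 10. Entries are P(too toxic) at a true 3% / 9%.

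| Evaluable | Percentage form: events needed | Percentage form | Count form (≥ 10) |
|---|---|---|---|
| 104 | 6 | 0.093 / 0.915 | 0.001 / 0.462 |
| 117 | 6 | 0.141 / 0.958 | 0.003 / 0.615 |
| 119 | 6 | 0.149 / 0.962 | 0.003 / 0.637 |
| 120 | 7 | 0.070 / 0.923 | 0.003 / 0.647 |
| 130 | 7 | 0.097 / 0.954 | 0.006 / 0.742 |
| 180 | 10 | 0.046 / 0.967 | 0.046 / 0.967 |

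Over 104 to 130 the percentage form runs from 0.070 to 0.149 at 3% and from 0.915 to 0.962 at 9%. The count form detects a true 9% with chance 0.46 to 0.74.

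**4. How much is due to the shortfall.** The jump from 0.149 at 119 to 0.070 at 120 comes from the whole-number cutoff. Full accrual would show the same sawtooth: over 160 to 200 evaluable (80% to 100% of 200) the percentage form gives 0.040 to 0.092 at 3%. The unweighted means are 0.066 over 160 to 200 and 0.105 over 104 to 130, an average rise of 0.039.

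**5. Where the two wordings part.** At 117 they disagree for 6 to 9 events (6/117 = 5.1%, 9/117 = 7.7%); at 130, for 7 to 9 events (7/130 = 5.4%, 9/130 = 6.9%). Chance of such a count:

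| True rate | n = 117 | n = 130 |
|---|---|---|
| 3% | 0.14 | 0.09 |
| 5% | 0.46 | 0.36 |
| 6% | 0.54 | 0.41 |
| 7% | 0.53 | 0.39 |
| 9% | 0.34 | 0.21 |

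**6. Intervals.** For 9/180 the two-sided exact (Clopper-Pearson) interval is 2.31% to 9.28%, as stated. For 0/180 the one-sided 95% bound is 1 − 0.05^(1/180) = 1.65%, which is the stated 1.7%. The two-sided exact limit is 1 − 0.025^(1/180) = 2.03%. With 0 events the two-sided upper limit would be 3.1% at 117 and 2.8% at 130.

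**The case against.** The strongest reply is that a planning calculation describes the planned size, that this one is correct, and that early closure does not make it defective. That stands: there is no arithmetic error in the error rates at 180.

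The second reply is that there is really one rule. The count only translates 5% at an expected 180, so the percentage is what carries over. A fixed count would accept 9/117 = 7.7% under a sentence that sets the line at 5%. This also stands. A reader might infer from step 5 that two equal rules compete and that the verdict is close to a coin toss. The documents do not support that: the disagreement matters only if the count was in fact carried over, and the chances near 0.5 arise at true rates of 5% to 7%, between the design values. Under the percentage reading detection is nearly kept, and the change is mainly more false alarms, which err on the cautious side.

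The third reply is that the shortfall is inferred. The closure entry reports a later event and is not superseded design text, but the contents of Amendments #40 and #46 are not supplied, and no section gives the final 40 Gy count. The number treated may also be below 130, since Section 5.1.3 provides that if the radiation oncologist is "unable to devise a dosimetrically-satisfactory treatment plan, then the patient will be removed from study". If 330 means analysable patients and the lower cohorts lost some, 130 is not a strict ceiling. But 180 at 40 Gy would then require the lower cohorts to supply only 330 − 180 = 150 of their 200. If they supplied 180, the remaining 150 would give 0.083 / 0.965 by percentage and 0.016 / 0.877 by count, still not the stated pair.

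On the zero-event interval, putting all 5% in the upper tail is a recognised choice, but it should be labelled as such beside a two-sided interval.

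**Conclusion.** The point holds as one of restating and reporting, between minor and should-fix. The pair 0.05 and 0.97 is right for 180 to about 185 evaluable patients and does not apply at about 130 treated. Under the natural percentage reading, with 104 to 130 evaluable, the false-alarm chance at 3% is 0.07 to 0.15 (0.141 at 117, 0.097 at 130; on average 0.105 against 0.066 at 160 to 200), and part of that spread is the whole-number cutoff. Detection at 9% is 0.91 to 0.96. Only if the count of more than 9 was kept does detection fall to 0.46 to 0.74.

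This assumes that the 330 include about 100 patients at each lower dose and that 80% to 100% of the 40 Gy patients are evaluable at 3 years. A reader might go further and infer that the sponsor ignored the shortfall or has no rule for it. The documents cannot show that, since a revised rule may lie in material not supplied. Separately, 0 to 1.7% for 0 of 180 is a one-sided bound given as a 95% interval.

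**What to change.** - State how many patients were treated at 40 Gy and how many were evaluable at 3 years.
- Reconcile the percentage and count wording: say which form was applied and when that was decided. If no decision is on record, show the result under both. Do not present a later choice as prespecified; with closure effective 10/13/10, every 3-year window had ended by about October 2013.
- Replace 0.05 and 0.97 with exact binomial error rates for the achieved number and the form applied.
- Report the observed rate with a two-sided exact 95% interval.
- Correct the interval for 0 of 180 to 0 to 2.0%, or label 1.7% as a one-sided bound.

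The cost is a short clarification or reporting note. The stated error rates become less favourable, the interval is wider, and the verdict may have to be shown as depending on the form of the rule. No more patients are needed.

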6.2 Reporting Adverse Events

6.2.1 Reporting Acute and Sub-acute Noncutaneous Toxicity: Any acute or subacute noncutaneous toxicity of grade 2 or higher according to the NCI Common Toxicity Criteria version 3.0 should be reported within 48 hours by telephone and within 7 working days in writing (by mail, fax or e-mail)

To: [name], PhD
Department of Radiation Oncology
Massachusetts General Hospital
[name]
[name]
[name]
[contact]
[contact]
Email: [contact]

[name]
Cancer Center Protocol Office
Massachusetts General Hospital
[name]
[name]
[contact]
[contact]
Email: [contact]

6.2.2 Chronic Toxicity: Any chronic toxicity of the skin or subcutaneous tissues of grade 4 or higher or the development of fat necrosis (see

APPENDIX 2) or other complication requiring surgery should be reported to [name] within 48 hours by telephone and within 7 working days.

6.2.3 Poor Cosmetic Results: Any fair or poor cosmetic results (see APPENDIX 3) should be reported to [name] within 48 hours by telephone and within 7 working days in writing the first time that this is observed.

6.2.4 Reporting Events to the Office for the Protection of Research Subjects (OPRS): The following events need to be reported to the Dana Farber Cancer Institute Institutional Review Board (IRB):

- Grade 2 (moderate) and Grade 3 (serious events) – Only events that are Unexpected and Possibly, Probably, or Definitely Related/Associated with the Intervention (PBI)
- All Grade 4 (life-threatening) events – unless mentioned otherwise in this protocol
- All Grade 5 (fatal) events – When the patient is enrolled and actively participating in the trial or when the event occurs within 30 days of the last study intervention

6.2.4.1 Full written SAE report must be submitted to OPRS as soon as possible, but no later than 10 working days from notification of the event.

6.2.4.2 If the patient is in long-term follow up, death may be reported at the time of continuing review.

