either stage) had been noted to have a bad event. Using this design, there was a 59% chance of terminating accrual during the first stage if the true rate of a bad event is 15% and a 9% chance if the true rate of a bad event is 7%. There was a 5% chance of deeming the treatment feasible if the true rate of a bad event is 15% and an 80% chance if the true rate of a bad event is 7%. We have not yet had 34 patients followed for at least 1 year on the first dose (this will occur in July 2005), and at this early time there is no reason to think that the 32 Gy dose is associated with unacceptable toxicity.

A dose level will be deemed infeasible if too many patients have at least one of the following outcomes:

- a) The patient has a breast cancer recurrence (local, regional, or distant) within 1 year of protocol registration (since this will necessitate her removal from study, see section 5.1.4).
- b) The patient dies from causes judged to be related to her treatment within 1 year of protocol registration.
- c) The patient develops fat necrosis or other grade 4 skin or grade 4 subcutaneous toxicity or requires surgery for her skin or subcutaneous toxicity within 1 year of protocol registration.

In the rest of this section, a patient who has at least one of these 4 outcomes is said to have “a bad event.”

We will continue to use a two-stage design for each of the three dose-levels. With the increased accrual rate, at the time the decision has to be made on whether to increase the dose level, there will be 50 patients who have been followed for at least 1 year. We have therefore changed the size of the first stage of accrual to 50 patients (and made the size of the second stage 50 patients, in order to keep the maximum number of patients at each dose-level at 100).

Since the decision to increase the dose will be based on the results in the first 50 patients, and since higher doses might have higher toxicity rates, we have also changed the probabilities of the null and alternative hypotheses for the first two doses to 13% and 5%, respectively. For the third and final dose-level, the null and alternative hypotheses are unchanged at 15% and 7%, respectively.

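### The 40 Gy fat-necrosis rule is written on an expected 180 patients; other sections count all 200, and the text does not say whether 5% or 9 governs at another number

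*Combined protocol and SAP*

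**What the plan says.** Section 10.0 makes fat necrosis requiring surgery within 3 years of registration the primary endpoint of the expanded 40 Gy cohort, and combines all 200 patients of that cohort for analysis. It then gives an expectation: "We expect that 90% of the 200 patients will be available for assessing fat necrosis for 3 years after registration". The other 20 patients are those who leave early for one of four reasons, namely recurrence, metastases, death or loss to follow-up. The decision rule follows: the dose is too toxic "If more than 5% of the 180 patients (i.e., more than 9 patients) have fat necrosis requiring surgery by 3 years after registration". The stated chance of that verdict is 0.05 at a true risk of 3% and 0.97 at 9%.

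Two other places define the endpoint without reference to availability. Objective 2.1(d) reads "Within 3 years of protocol registration, the patient treated with 40 Gy develops fat necrosis requiring surgery" and has no exclusion for early exit. The last paragraph of Section 1.3 says that everyone who receives 40 Gy, given as 200 patients, enters the analysis of this endpoint.

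On numbers, Section 1.3 reports 100 patients at 32 Gy and continues: "At this time, we have accrued 100 patients to the second cohort and 94 patients to the third cohort". The status log at the front records permanent closure to accrual in October 2010: "Analysis will proceed w/ data collected from 330 pts".

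**The concern.** The rule uses a forecast as its denominator, and this leaves two things open.

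- **Who is counted.** The 180 are what remains after removing patients who recur, develop metastases, die or are lost before 3 years. A woman who has surgery for fat necrosis at 12 months and recurs at 30 months belongs to the other 20, so on the literal wording her event is not in the rule. Section 1.3 and Objective 2.1(d) would count her. No section says how an early exit enters the numerator or the denominator, and no censoring or time-to-event method is given.
- **What the limit is when the number is not 180.** Five per cent and nine patients are the same limit at 180. They separate elsewhere, and the text does not say which one governs.

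This rule gives the primary verdict on 40 Gy. If the choice between the two forms is left until the data are in, it could be made with the count already known.

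**Working it through.** **Inputs.** From Section 10.0: 200 planned, 90% available (200 × 0.90 = 180), limit more than 9 (at least 10), true risks 3% and 9%. From Section 1.3 and the status log: 330 − 100 − 100 = 130 at 40 Gy, and 130 × 0.90 = 117 available. The 130 and 117 are inferences. No section gives the final 40 Gy count.

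**Step 1: the plan's own figures.** With X ~ Binomial(180, p), P(X ≥ 10) = 0.046 at 3% and 0.967 at 9%. These match the stated 0.05 and 0.97. The exact 95% interval for 9/180 is 2.3% to 9.3%, also as stated. The figures are correct for exactly 180 patients.

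**Step 2: other numbers available.** The count form needs X ≥ 10. The percentage form needs X > 0.05n.

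| n | 9/n | Count: 3% / 9% | Percentage needs | Percentage: 3% / 9% |
|---|---|---|---|---|
| 180 | 5.0% | 0.046 / 0.967 | ≥ 10 | 0.046 / 0.967 |
| 160 | 5.6% | 0.023 / 0.918 | ≥ 9 | 0.053 / 0.957 |
| 130 | 6.9% | 0.006 / 0.742 | ≥ 7 | 0.097 / 0.954 |
| 117 | 7.7% | 0.003 / 0.615 | ≥ 6 | 0.141 / 0.958 |

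At 117, any result from 6 to 9 surgeries gives opposite verdicts under the two forms. The chance of that is 0.141 − 0.003 = 0.138 at 3%, 0.534 − 0.069 = 0.465 at 5%, and 0.958 − 0.615 = 0.343 at 9%.

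**Step 3: surgeries before early exit, at the planned size.** Assume that 20 of 200 leave, independently of toxicity, with exit and surgery times uniform over 3 years. A leaver then has on average half of the 3-year risk before leaving. The expected number of omitted surgeries is 20 × 0.5 × p, which is 0.3 at 3%, 0.5 at 5% and 0.9 at 9%. The chance of a too-toxic verdict is:

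| True risk | 180 only, ≥ 10 | All observed, ≥ 10 | Opposite verdicts | All observed, more than 5% of 200 (≥ 11) |
|---|---|---|---|---|
| 3% | 0.046 | 0.062 | 0.016 | 0.03 |
| 5% | 0.413 | 0.480 | 0.067 | 0.35 |
| 9% | 0.967 | 0.980 | 0.013 | 0.96 |

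Counting the omitted surgeries makes the verdict slightly easier to reach if the limit stays at 9, and slightly harder if 5% is applied to all 200. The direction depends on the denominator.

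**The case against.** The strongest reply is that the rule is a percentage, and that the 9 in brackets only translates 5% at the planned number. Objective 2.1 is also framed as a percentage of patients. This is the more natural reading, and it stands. A reader might infer from the table that the plan would miss a true 9% risk in almost 4 trials of 10. That holds only if the count governs at 117. On the percentage reading the chance of detection stays near 0.96. What the reply does not remove is the false-alarm rate of 0.141 at 117 against a stated 0.05, or the lack of any sentence saying which form applies.

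Secondly, Section 1.3 and the pooling sentence in Section 10.0 suggest that surgeries before early exit were meant to count, and a woman who has had the surgery has in effect been assessed. This also stands in part. The documents do not show an intention to drop these events. They show two populations, 180 and 200, for one endpoint.

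Thirdly, the early-exit effect is small at the design rates. The largest figure, 6% to 7%, arises at a true risk equal to the limit, where neither verdict is clearly wrong. That is fair.

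Fourthly, closing early is not a flaw in the design, and the log entry does not contradict the protocol. Agreed: it only indicates the number the rule is likely to meet. Without it, any number available other than about 180 still separates the two forms, by less (0.918 against 0.957 at 160 and 9% true risk).

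**Conclusion.** The concern holds as a conflict over the analysis population and an unspecified limit. It is not an error in the stated probabilities, which are right for 180.

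- **Early exits:** a modest effect at the planned size, about 1% to 2% opposite verdicts at 3% and 9% true risk and 6% to 7% at 5%. This assumes exits unrelated to toxicity and a limit kept at 9. A reader might infer that the wording always makes a too-toxic verdict harder to reach. Step 3 shows that this is not general.
- **Number available:** the larger issue. At 117 the stated 0.05 and 0.97 hold together under neither form. The count loses detection (0.615), and the percentage nearly triples the false-alarm rate (0.141). This rests on 330 being the total over all dose levels, 100 in each of the first two, and the plan's own 90%.

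Confidence is high on the arithmetic and on the silence of the text, and lower on 117 as the actual number.

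**What to change.** Reconcile Section 1.3, Objective 2.1(d) and Section 10.0 as follows.

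1. Count every observed surgery for fat necrosis within 3 years of registration in any patient treated at 40 Gy.
2. Estimate the 3-year cumulative incidence in all of them. Censor losses at last contact. Treat death and removal of the treated breast as competing events. Keep patients with recurrence or metastases at risk while they are followed.
3. State that the 5% limit governs, applied to that estimate, and that 9 is only its value at 180. Report the confidence interval.
4. Keep the proportion among available patients as a sensitivity analysis.
5. Restate the error rates for the number actually treated at 40 Gy.

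Item 2 needs one related clarification. Section 10.0 says of any recurrence within a year "since this will necessitate her removal from study, see section 5.1.4", but Section 5.1.4 prescribes removal only for recurrence during treatment. These passages must be reconciled so that it is clear whose follow-up for this endpoint continues. Censoring at removal would work against item 1.

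The cost is a few sentences and a standard analysis. Section 7.0 provides six-monthly follow-up for 5 years, and Section 6.2.2 requires that fat necrosis "or other complication requiring surgery should be reported to" a named recipient within 48 hours. Whether the data forms hold a surgery date cannot be seen in the text, so this should be checked. The downside is a slightly more complex analysis and less favourable stated error rates. By simulation with 10% leaving, the chance of a too-toxic verdict with 130 treated is about 0.07 to 0.09 at 3% and 0.93 to 0.94 at 9%, depending on how exits are classed.

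### Do the two 95% intervals given for fat necrosis at 40 Gy need correcting because they are built on different bases?

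*Combined protocol and SAP*

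**What the plan says.** Section 10.0 (Accrual Goal and Statistical Power) enlarges the third cohort to 200 patients and narrows its endpoint: "Our primary endpoint for this expanded cohort will be limited to fat necrosis requiring surgery within 3 years of protocol registration". On follow-up it says: "We expect that 90% of the 200 patients will be available for assessing fat necrosis for 3 years after registration", which gives 180. The decision rule is a count. The dose is judged too toxic "If more than 5% of the 180 patients (i.e., more than 9 patients) have fat necrosis requiring surgery by 3 years after registration", with a stated chance of 0.05 of that verdict if the true rate is 3% and 0.97 if it is 9%.

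The section then illustrates precision for two possible results. The first begins "If none of the 180 patients have this toxicity" and continues "the 95% confidence interval (CI) for the probability of fat necrosis requiring surgery will be 0 to 1.7" percent. The second reads "if 9 of the 180 patients have this toxicity, a 95% CI will be 2.3 to 9.3" percent. Neither the method nor the sidedness is given for either interval, and I found neither elsewhere in the document.

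**The concern.** Two intervals in one sentence, for one endpoint and under one name, would normally be read as the same kind of interval. They are not. The interval for 9 of 180 leaves 2.5% in each tail; the limit for 0 of 180 leaves 5% in the upper tail. Read beside its companion, the zero-event figure looks tighter than a like-for-like interval would be, and on a safety endpoint that errs in the favourable direction.

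Two further worries follow. A rule that switches convention only when no events occur does not hold 95% coverage at every true rate. And because the plan names no method, whoever reports the endpoint could choose one after seeing the data. The front-sheet log makes a recalculation certain: accrual closed early and "Analysis will proceed w/ data collected from 330 pts", fewer than the 400 shown in the protocol schema.

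**Working it through.** **Inputs.** All from Section 10.0: n = 0.90 × 200 = 180 evaluable patients; example results of 0 and 9 events; stated intervals 0 to 1.7% and 2.3 to 9.3%; decision rule X > 9.

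**Step 1: reproduce the plan's intervals (exact binomial limits).** For x events in n, with tail area a on each side, the lower limit is the a quantile of Beta(x, n − x + 1) and the upper limit is the 1 − a quantile of Beta(x + 1, n − x). For x = 0 the lower limit is 0 and the upper limit reduces to 1 − a^(1/n).

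| Result | a = 0.025 | a = 0.05 | Plan states |
|---|---|---|---|
| 9/180 | 2.31 to 9.28% | 2.63 to 8.56% | 2.3 to 9.3% |
| 0/180, upper limit | 1 − 0.025^(1/180) = 2.03% | 1 − 0.05^(1/180) = 1.65% | 1.7% |

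The first stated interval matches only the a = 0.05 column and the second only the a = 0.025 column. The rule of three, 3/180 = 1.67%, also rounds to 1.7%.

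**Step 2: could one method give both?** None of those tried does.

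| Method (95%) | 0/180, upper limit | 9/180 |
|---|---|---|
| Mid-P | 1.65% | 2.47 to 8.98% |
| Wilson | 2.09% | 2.65 to 9.23% |
| Agresti-Coull | 2.51% | 2.52 to 9.36% |
| Jeffreys | 1.38% | 2.50 to 8.93% |
| Likelihood ratio | 1.06% | 2.43 to 8.83% |
| Blaker | 1.97% | 2.53 to 9.23% |
| Sterne | 2.08% | 2.53 to 9.35% |

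Wald and Crow/Blyth-Still type intervals do not match both either. The mixture of conventions is real, and rounding does not explain it.

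**Step 3: size.** 2.03% − 1.65% = 0.38 percentage points at n = 180.

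**Step 4: does the decision rule depend on it?** With X ~ Binomial(180, p), P(X > 9) = 0.046 at p = 3% and 0.967 at p = 9%. These agree with the stated 0.05 and 0.97, and no confidence limit enters the calculation.

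**Step 5: coverage if the mixture were used as a procedure.** Take 1.65% as the limit at zero events and Clopper-Pearson otherwise. Just above a true rate of 1.65%, the interval misses when X = 0 (probability 0.050) or X ≥ 8 (probability 0.011), so coverage is 1 − 0.050 − 0.011 = 0.939. It stays below 0.95 until 1.94%, the lower limit for 8/180. Clopper-Pearson throughout stays at or above 0.950 on a grid of true rates up to 10%.

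**Step 6: the number likely to be analysed.** The documents do not give the evaluable number at 40 Gy. Assume the cohorts filled in order; the schema numbers patients that way, and Section 1.3 reports "we have accrued 100 patients to the second cohort and 94 patients to the third cohort". Then 330 − 200 = 130 patients received 40 Gy, and 90% of those is 117. Zero-event upper limits would be:

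| Evaluable | Two-sided exact | One-sided exact |
|---|---|---|
| 100 | 3.62% | 2.95% |
| 117 | 3.10% | 2.53% |
| 130 | 2.80% | 2.28% |

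**The case for a change.** The strongest case for a change is that this sentence is the plan's only statement of the precision expected for a primary safety endpoint. A few words would make it consistent, and naming a method now would remove a choice made after the data are seen. The gap also widens as the evaluable number falls: at 117 patients it is 3.10 − 2.53 = 0.57 percentage points.

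The arithmetic behind this stands, and so does the observation that the label is incomplete. The inference that a number must be replaced does not. The lower limit at zero events is 0 whatever the method, so there is no second tail to protect, and putting all 5% above is a recognised convention. On that view each stated interval carries a total tail allowance of 5%. Whether to print 1.7% or 2.0% is a matter on which competent statisticians differ.

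The coverage argument tests a procedure the plan never prescribes. Section 10.0 illustrates two outcomes; it does not set a switching rule for the final report. Even under that rule the loss is about one percentage point, confined to true rates of 1.65 to 1.94%, below both design rates.

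The analyst's freedom is narrow too. It matters only if no events are seen, and then the choice is between two standard limits, either of which a report would normally identify.

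**Conclusion.** No change to the plan is needed. Section 10.0 places a one-sided 95% upper bound (1.65%, printed as 1.7%) beside a two-sided exact 95% interval without saying so. Each figure is correct on its own basis. What is missing is a label, and any competent report of the result would supply it.

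The difference is 0.38 percentage points at 180 patients. Limits of 1.7% and 2.0% both lie below the 3% design rate and the 5% cut-off, so the reading of a zero-event result at that size is the same. The sample size, the toxicity rule, its two stated probabilities and the one-year stopping rule use neither interval.

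Early closure means that the 180-patient figures will not be the ones reported, so editing them would alter no result. At the assumed 100 to 130 evaluable patients the zero-event limit would be 2.8 to 3.6% two-sided or 2.3 to 3.0% one-sided. Those ranges fall on either side of 3% but remain below the 5% cut-off, and the decision is still made on the event rate rather than on a limit. They rest on two assumptions the documents do not confirm: that the cohorts filled in order, and that about 77 to 100% of 130 patients are evaluable (100/130 to 130/130).
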